Focused lung ultrasound for diagnosing and risk- stratification of patients with COVID-19 symptoms

April 8, 2020
NCT 04327674

Background

COVID-19 is defined as an infectious disease caused by SAR-CoV-2 virus. It results in pneumonia and sometimes respiratory failure. SARS-CoV-2 pandemic has led to massive strain on health care facilities. A large proportion of the population is at risk of COVID-19 and some estimates suggest that up to 15% will need hospitalization. Such number of patients strains the health care system to its maximum as capacity has limitations even in highly developed countries.

Early reports estimate that more than 80% of patients admitted to hospital with COVID-19 have abnormal findings on chest radiographs¹. Thus, imaging seems to be an important part of the diagnostic work-up. In most hospitals however, access to CT-scanning of the thorax of all patients with COVID-19 or with suspicion of COVID-19 is unrealistic due to restricted capacity. Chest radiographs are faster and easier to do, but may require transportation of the patient to the department of radiology which carries a risk of virus spreading in the hospital. On-site chest radiograph is often of such low quality that diagnosis or follow-up will be difficult.

Focused ultrasound examination of the lungs, FLUS, is a diagnostic tool that can show changes in the lung parenchyma due to pneumonia. FLUS is a bed-side examination performed by the physician which results in reduced risk of in-hospital virus contamination. Furthermore, results from FLUS are immediately available to the physician. This allows rapid decision-making which is essential in cases of high patient burdens as seen in the COVID-19 pandemic.

Furthermore, SARS-CoV-2 positive patients with pneumonia may be at higher risk of respiratory failure than those without pneumonia. Identifying patients at high risk can qualify decisions about monitoring level and organization of intensive care resources. Conversely, patient with COVID-19 symptoms but without pneumonic FLUS finding could likely be managed as out-patients. Such a risk-stratification may optimize the allocation of limited healthcare resources and reserve in-hospital capacity to those patients who needs it.

Hypothesis

FLUS can risk-stratify patients with COVID-19 symptoms.

FLUS can predict respiratory failure in patients with COVID-19 pneumonia.

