FLUS can diagnose COVID-19 pneumonia with high sensitivity and specificity using PCR-test and chest radiograph as reference.

Aim

To study the ability of FLUS in COVID-19 to predictive respiratory failure.

To study the diagnostic capability of FLUS to find COVID-19 pneumonia.

To study risk-stratifying capability of FLUS in patients with COVID-19 symptoms.

Method

Design

Multicenter prospective cohort study with convenience sampling.

Setting

Emergency departments or internal medicine departments who admit patients with COVID-19 symptoms.

Participants

Patients who have COVID-19 symptoms and require diagnostic testing.

Patients who have a positive SAR-CoV-2 PCR-test and require admission to hospital.

Inclusion criteria

- Patients who are seen in COVID-clinics or emergency departments due to symptoms that require diagnostic work-up to COVID-19.
- Patients admitted to hospital with positive SARS-COV-2 PCR-test and in whom FLUS is performed less than 48 hours after admission.

Exclusion criteria

- Age less than 18 year.
- Former participation in this study.
- Pre-FLUS ventilator support.

Double inclusion

Inclusion in this study will not restrict patient from inclusion in other studies.

Recruitment

Participants are recruited at the local hospital. In Denmark the study is labelled quality assurance and the need for informed consent is thus waived. Local regulations are followed and it is the responsibility of each inclusion site to achieve appropriate regulatory permissions including need for approval from local ethical committees and healthcare authorities.

Variables

Ultrasound variables: FLUS are performed according to ERS guidelines and to Standard of Operating Procedure specific to this study. Film clips are recorded and saved for later evaluation. 14 zones are scanned. Film clips are marked with scanning position (L1, L2...etc.). If the patient is unable to sit, only anterior and lateral zones are scanned. FLUS findings are assessed on the film clips by an observer blinded to other variables. Findings are coded with 1/0 for presence of pneumonia. Moreover, a scoring system is applied:

FLUS findings	Score
Normal FLUS	0
Interstitial syndrome, defined as more than 3 B-lines in a single zone.	1
Diverse B-lines or irregular pleura	
Interstitial syndrome, defined as more than 3 B-lines in a single zone.	2
Confluent B-lines.	
Consolidations (sub-pleurale, lobar, with or without air-bronchograms)	3

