Data on FLUS operator: Level of medical degree. Years of experience with lung ultrasound. Completed training in FLUS.

From patient files the following data is extracted:

Patient demographic: Sex, age, height, weight, co-morbidities.

Clinical data on time of admission: Blood pressure, pulse, peripheral saturation, respiratory frequency, temperature, length of illness, list of symptoms, limitation to treatment i.e. not suited or willing to intensive care treatment and intubation.

Data from radiographic diagnostics: Result of chest radiograph, CT or HRCT scanning, if done for clinical reasons. No further review of radiographic examinations is performed. Results given by local radiology department is used.

Microbiological data: Result of SARS-CoV-2 PCR-test from nasal/oral/laryngeal or tracheal samples.

Data from admission: Time of admission. Place of admission. Time of dismissal. Admission to intensive care. Intubation. Time in ventilator. Death, survival. In hospital survival, 14- and 30-days survival.

Endpoints

Primary endpoint: FLUS (binary: positive/negative pneumonia) related to intubation (yes/no).

Secondary endpoints: Relationship between FLUS and SARS-CoV-2 PCR result.

Relationship between FLUS and radiographic findings.

Relationship between FLUS and admission to intensive care (not intubation).

Relationship between FLUS and re-admission (Patient returning to emergency department or COVID-clinic).

Scores of FLUS findings in different zones.

Data management

The study uses convenience sampling as FLUS may not be available at all times. FLUS is performed by the clinician such that only doctors with clinically relevant work are allowed to scan the patient. This minimizes the risk of disease transfer to doctors and reduces the use of protection equipment.

Ultrasound film clips are recorded according to standard operating procedure. Film clips are stored securely, according to local legal regulations. All variables extracted from patient files are stored in an eCRF using REDCap supplied by Aarhus University Hospital.

Every site will have access to enter data in data capture instruments. Access to REDCap is managed by the project steering committee at Aarhus University Hospital.

Data analysis

All data are analyzed in Stata.

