Binary endpoints, including primary endpoint, are analyzed using Chi-2 test. Continuous data are assessed for parametric distribution and analyzed with Student's T-test on logarithmic transformed data in case of non-parametric distribution.

Level of statistical significance is set to 5%.

A logistic prediction model will be developed. Dependent variable is intubation. Independent variables are age (continuous), FLUS result (Binary or ordinal), SARS-CoV-2 status (Binary) and peripheral oxygen saturation (continuous).

The data set will be divided in two. One is used for model development and one is used for validation of the model. Geographic external validity is tested. Internal validity is tested with bootstrapping method. Sensitivity, specificity and ROC AUC is calculated.

Sample size

No prior publications are available for sample size estimation.

For the prediction model we wish to include 10-15 events per independent variable, 50-75 events. From early estimations about 20% of admitted patients requiring intubation our estimate is 375-400 participants.

Inclusion period

An end date is set to May 15 2020. If COVID-19 pandemic is ongoing at this time point the study may extent.

Blinding

Ultrasound film clips are analyzed blinded to other variables.

Plan for publication

Data analysis is estimated to end July 1. 2020. Article submission is estimated to October, 2020.

Preliminary data analysis

Available data will be analyzed soon after 15. May.

Ethical considerations

FLUS is without any risk to patients. COVID-19 is an infectious disease and isolation is needed. Contamination during the study needs to be avoided. For this reason, FLUS is only performed by the physicians who are required to see the patient regardless of this study. The ultrasound equipment is cleaned after each examination in accordance with local guidelines.

Legal regulations

In Denmark the study is classified as a quality assurance project. Arrangements and permission to access to patient files in each site is required. According to guidance from the legal office at Region Midt a data management agreement is not needed.

International data agreements are required to data transfer from international sites to Denmark.

All international sites must adhere to local regulation. Responsibility of this is on the international site.

Publication

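### The single pooled FLUS-by-intubation chi-square suits the all-symptomatic-patients aim, but cannot by itself support prediction of respiratory failure in COVID-19 patients

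*Protocol*

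**What the plan says.** The Inclusion criteria open two routes into the study:

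- Work-up route: "Patients who are seen in COVID-clinics or emergency departments due to symptoms that require diagnostic work-up to COVID-19". PCR status is still open and admission is not required.
- Inpatient route: "Patients admitted to hospital with positive SARS-COV-2 PCR-test and in whom FLUS is performed less than 48 hours after admission". Everyone is admitted and PCR-positive by definition.

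The design is a "Multicenter prospective cohort study with convenience sampling", with no target share for either route.

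The Endpoints section names no population for the primary endpoint: "Primary endpoint: FLUS (binary: positive/negative pneumonia) related to intubation (yes/no"). Under Data analysis, "Binary endpoints, including primary endpoint, are analyzed using Chi-2 test". Neither document restricts or stratifies that test.

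The objectives name different populations. Hypothesis 1 reads "FLUS can risk-stratify patients with COVID-19 symptoms", and aim 3 matches it. Hypothesis 2 reads "FLUS can predict respiratory failure in patients with COVID-19 pneumonia", and aim 1 reads "To study the ability of FLUS in COVID-19 to predictive respiratory failure". The documents do not say which of these the primary endpoint serves.

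The protocol also plans a logistic model for intubation with age, FLUS, SARS-CoV-2 status and saturation. The SAP's ventilator model has mean FLUS score, age, sex and saturation, in patients without a ventilator treatment limit. Its Building Prediction Models section lists sex, age, comorbidity, oxygen and mean FLUS score. Neither SAP list has SARS-CoV-2 status, and no planned model has entry route.

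The relationship of FLUS to PCR is a secondary endpoint with no population named. The diagnostic hypothesis speaks of sensitivity and specificity.

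**The concern.** Suppose admitted patients have both more positive scans and more intubations than patients who are not admitted. The pooled table then shows an association even if the scan says nothing about intubation among admitted patients, or among the others. For risk stratification of everyone with symptoms, that association is real information, although its size depends on the mix. For prediction among patients who have COVID-19, it may only restate who was admitted. A significant result could be reported as meeting aim 1 when it does not.

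The FLUS-PCR comparison has a related problem. Inpatients enrolled on a positive PCR are selected on the reference result. They add PCR-positive patients and no PCR-negative ones, so pooled sensitivity follows the mix whenever it differs by route.

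**Working it through.** **The plan's own figure.** Sample size: 75 events / 0.20 = 375 participants, the lower stated figure; 400 corresponds to 80 events. The 20% is an intubation risk in admitted patients. No power is given for the chi-square.

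**Inputs.** From the documents: 400 participants, 20% intubation if admitted, 5% significance level. Assumed, because the documents do not give them:

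- 140 not admitted, 60 admitted through work-up with PCR pending, 200 PCR-positive inpatients;
- non-admitted intubation of 3%, 10% or 20%;
- FLUS positivity by admission group, as in the table below;
- no FLUS-intubation association within either admission group.

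**How mixing creates an association.** Pooled risk in FLUS-positives = (sum over groups of n × positivity × risk) / (sum of n × positivity), and likewise for negatives. At 3% non-admitted risk and positivity 20/80 (not admitted/admitted):

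- FLUS-positive: (140×0.2×0.03 + 260×0.8×0.20) / (28 + 208) = 42.44/236 = 18.0%
- FLUS-negative: (140×0.8×0.03 + 260×0.2×0.20) / (112 + 52) = 13.76/164 = 8.4%
- Odds ratio = (0.180/0.820) / (0.084/0.916) = 2.4, against 1 within each group.

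**Chance of a significant pooled test** (20,000 simulated cohorts per cell, Pearson chi-square without continuity correction):

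| Non-admitted intubation | 50/50 | 40/60 | 30/70 | 20/80 |
|---|---|---|---|---|
| 3% | 5% | 14% | 44% | 80% |
| 10% | 5% | 8% | 16% | 32% |
| 20% | 5% | 5% | 5% | 5% |

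The mix matters too. At 3% and 30/70, having 60, 140 or 260 non-admitted patients gives 15%, 44% or 60%.

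**What stratifying achieves** (Mantel-Haenszel test, same inputs, 3% non-admitted risk):

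- Whole cohort by entry route: about 7%, 14% and 32% remain significant at 40/60, 30/70 and 20/80, because the work-up route still mixes admitted and non-admitted patients.
- PCR-positive patients only, by entry route: 5-11% remain. This assumes 30% of the 140, 60% of the 60 and all 200 are PCR-positive, that is 42, 36 and 200 patients.

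**FLUS-PCR sensitivity.** Pooled sensitivity = (PCR-positives detected in both routes) / (all PCR-positives). Assume 80% sensitivity in inpatients, 50% in PCR-positive work-up patients, and 20% PCR-positive at work-up. With half the cohort inpatients: (0.5×0.80 + 0.5×0.20×0.50) / (0.5 + 0.5×0.20) = 0.45/0.60 = 75%. Inpatient shares of 0%, 25% and 75% give 50%, 69% and 78%. If sensitivity is equal in both routes, nothing moves. Specificity is unaffected, since the inpatient route contributes no PCR-negative patients.

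**The case against.** **The chi-square is not the only analysis.** No passage says it alone carries aim 1 or hypothesis 2, and the protocol's logistic model includes SARS-CoV-2 status and saturation. This stands in part: the model can absorb some of the mixing. But it lacks entry route, has no estimate confined to COVID-19 patients, and loses SARS-CoV-2 status in the SAP. The SAP's outcome, COVID-19-related ventilation, narrows the events but not the denominator, so PCR-negative patients would mostly enter as non-events. A reader might infer that the SAP's prediction model has been shown to be biased. It has not: the documents give too little to simulate that model with its oxygen and comorbidity terms.

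**A between-group difference is information.** This stands for hypothesis 1 and aim 3. A reader might call the 80% a false-positive rate; for the broad aim it is detection of a real marginal association.

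**Predictive values are at risk.** This is tempting, since they depend directly on the mix. But the documents do not plan them, so it is only a caution should they be reported.

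**Stratifying by admission status would settle it.** The documents do not support this. If work-up patients are scanned before it is decided whether they stay, admission status at the scan equals entry route. Later admission may be influenced by the scan, because the protocol's Background has the clinician acting on it at once. Blinded reading of the clips does not change that.

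**The inputs are assumed.** They are, and the range includes no distortion at all.

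**Conclusion.** The concern holds as a limit on what the pooled test can show. It fits hypothesis 1 and aim 3, but cannot by itself support aim 1 or hypothesis 2. That follows from the two entry routes and the unrestricted test, without any assumed figure. The size does rest on assumptions: admission mix, non-admitted risk and FLUS positivity. Across them the pooled test is significant in 5% to 80% of cohorts with no association within admission group, and at the nominal 5% when the two groups share the same risk or the same positivity.

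For FLUS-PCR, the problem in a planned measure is confined to sensitivity, and arises only if sensitivity differs by route. The plan should be changed, but the change is an added analysis and clearer wording, not a replacement of the primary test.

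**What to change.** 1. State that the pooled chi-square serves hypothesis 1 and aim 3, and keep it.
2. For aim 1, pre-specify the FLUS-intubation odds ratio with 95% CI in patients whose final PCR is positive, stratified by entry route (work-up or PCR-positive inpatient), and show the table for each route. Say that this reduces the mixing but may not remove it, and do not rely on admission status alone. In the SAP ventilator model, keep SARS-CoV-2 status as in the protocol and add entry route, subject to the events-per-variable rule.
3. Restrict any claim on hypothesis 2 to patients with COVID-19 pneumonia, and say how that pneumonia is established. If FLUS itself defines it, the binary predictor no longer varies.
4. Record in the eCRF whether PCR was known positive at enrolment. Estimate FLUS-PCR sensitivity, specificity and any predictive values only in patients whose result was unknown.

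**Cost.** Recruitment does not change; at most one eCRF field and some SAP wording are needed. The aim 1 estimate has fewer events and less power than the pooled test. Under the assumed inputs at 3%, events fall from 140×0.03 + 260×0.20 = 56.2 to 42×0.03 + 236×0.20 = 48.5.

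Adding two terms to the SAP's four-variable ventilator model makes six. At the SAP's 15 events per variable that is 90, more than the 75 expected from 375 participants even if all are admitted, so variables must be prioritised.

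The sensitivity interval widens. Around 75%, the Wilson 95% CI is 60-86% with an assumed 40 PCR-positives (30/40), against 69-80% with 240 (180/240).

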Statistical analysis plan.

Study name: The use of Focused Lung Ultrasound in Patients Suspected of COVID-19.

8.April 2020

Descriptive data:		
Demographic	Age	Mean, sd
	Sex	% kvinder
	Weight	Mean, sd.
	Height	Mean, sd.
	Site	groupe
Baseline data	BT sys	Mean, sd.
	BT dia	Mean, sd.
	SAT	Mean, sd.
	Puls	Mean, sd.
	Respiratory Rate	Mean, sd.
	Oxygen, l/min	Mean, sd.
	ferritin	Mean, sd.
	Hbg	Mean, sd.
	Leukocytter	Mean, sd.
	Lymfocytter	Mean, sd.
	Mono	Mean, sd.
	Neutrofile	Mean, sd.
	Egfr	Mean, sd.
	Karbamid	Mean, sd.
	Kreatinin	Mean, sd.
	Natrum	Mean, sd.
	Kalium	Mean, sd.
	Ddimer	Mean, sd.
	Probnp	Mean, sd.
	Tnt	Mean, sd.
	Tni	Mean, sd.
	glucose hba1c	Mean, sd.
	ph	Mean, sd.
	pco2	Mean, sd.
	po2	Mean, sd.
	be	Mean, sd.
	bicarbonat	Mean, sd.
	lactat	Mean, sd.
	Rtg af thorax	Grupper
	CT thorax	Grupper
	Covid-19 pcr	Yes/No
Treatment data	Antibiotica	Yes/No
	Antiviral	Yes/No

	Biological	Yes/No	
	Anti thrombotic	Yes/No	
	Death during admission	Yes/No	
	Length of admission	kontinuert	
	Death at 30 days	Yes/No	
	Cause of death	Covid/ikke-covid	
	Treatment restrictions, ITA	Yes/No	
	Treatment restrictions, ventilator	Yes/No	
FLUS data.	L1	0-3	
	L2	0-3	
	L3	0-3	
	L4	0-3	
	L5	0-3	
	L6	0-3	
	L7	0-3	
	R1	0-3	
	R2	0-3	
	R3	0-3	
	R4	0-3	
	R5	0-3	
	R6	0-3	
	R7	0-3	
	Flus mean	0-3, sd	
Inter- intraobservatør agreement			
Limits of agreement. Bland altmann.		20% Flus film re-scored by 1.observatør	Weigthed kappa kap s1 s2, tab wgt(w)
		20% Flus film scored by 2.observatør	Weigthed kappa kap o1 o2, tab wgt(w)
Mean Flus score related to event:			
Covid death	Parametric distribution qq plot and histogram		
	Norm +	t-test.	ttest flusmed, by(covdod)
	Norm -	Wilcoxon	ranksum flusmed, by(covdod)
			by covdod, sort : summarize flusmed, d graph bar (Mean) flusmed, over(covdod)
ITA admission	Parametric distribution qq plot and histogram		
	Norm +	t-test.	ttest flusmed, by(ita_in)
	Norm -	Wilcoxon	by ita_in, sort : summarize flusmed, d ranksum flusmed, by(ita_in)

			graph bar (Mean) flusmed, over(ita_in)
Ventilator treatment	Parametric distribution qq plot and histogram		
	Norm +	t-test.	ttest flusmed, by(respirator_beh)
	Norm -	Wilcoxon	by respirator_beh, sort : summarize flusmed, d ranksum flusmed, by(respirator_beh) graph bar (Mean) flusmed, over(respirator_beh)
Prædiction of event			
Covid death	Univariat logistical regression	Variable: covdod flusmed	
	Multivariate logistical regression	Variable: covdod, Flusmed, alder, køn, sat, ilt (kategori?)	

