ITA admission	Univariat logistiscal regression	Variable: ita_in flusmed	
	Multivariate logistical regression	Variable: ita_in, Flusmed, alder, køn, sat	, if behandlingsloft_ita ==0
Ventilator treatment	Univariat logistical regression	Variable: respirator_beh flusmed	
	Multivariate logistical regression	Variable: respirator_beh Flusmed, alder, køn, sat	, if behandlingsloft_resp ==0

Continuous variables are assessed for parametric distribution with quartile-quartile plots. Medians, interquartile ranges or means and standard deviations and ranges are reported according to parametric distribution. Students' t-test or Mann-Whitney U test is used as it was considered appropriate to evaluate differences between groups. The statistical significance is set to 5%. All data are handled in Excel (Microsoft) and REDCap (hosted at Aarhus University). All analyses are performed using Stata 14.2 (StataCorp, USA).

Building Prediction Models

Prediction models are based on multivariable logistic regression and preselected variables. The variables are sex, age, relevant comorbidity, oxygen administration and the mean-FLUS score. The selection of these variables is based on published data and clinical experience available to the study group during the study design stage. Explanatory variables are examined to decide cut-points, scales or the need for transformation. Variables are limited and prioritized to avoid overfitting or underfitting, respecting the study population size. Every included variable require at least 15 events.

The dependent variable is the primary outcome of interest: the COVID-19-related need for mechanical ventilation in the main analysis. Secondary outcomes are analyzed using the same logistic regression model, except for the outcome on high-flow oxygen treatment. The explanatory variable on oxygen administration is considered closely related to the outcome and is thus excluded from this analysis.

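### The SAP never carries out the protocol's primary analysis (binary FLUS against intubation by chi-square), and the ventilation model has three different specifications

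*Protocol*

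**What the plan says.** **Protocol.** Under Variables, each examination receives a binary code as well as the 0-3 score: "Findings are coded with 1/0 for presence of pneumonia". Under Endpoints, the plan is "Primary endpoint: FLUS (binary: positive/negative pneumonia) related to intubation (yes/no"). Under Data analysis, "Binary endpoints, including primary endpoint, are analyzed using Chi-2 test", at a 5% level. The same section adds a logistic prediction model with intubation as the dependent variable: "Independent variables are age (continuous), FLUS result (Binary or ordinal), SARS-CoV-2 status (Binary) and peripheral oxygen saturation (continuous"). The Sample size section is built on this model.

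**SAP, table.** The FLUS data are 14 zone scores, each 0-3, and their mean. For ventilator treatment the table gives a t-test, "ttest flusmed, by(respirator_beh"), or a rank-sum test if the mean score is not normally distributed. It then gives a univariable logistic regression on mean FLUS and a multivariable one: "Variable: respirator_beh Flusmed, alder, køn, sat". The multivariable model is restricted by `behandlingsloft_resp ==0`, that is, to patients without a ventilator limit.

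**SAP, Building Prediction Models.** "The variables are sex, age, relevant comorbidity, oxygen administration and the mean-FLUS score". On the outcome: "The dependent variable is the primary outcome of interest: the COVID-19-related need for mechanical ventilation in the main analysis".

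**The concern.** A SAP should tell the analyst how to produce the primary result that the protocol defines. This one does not. Someone working from the protocol would report a 2x2 table and a chi-square on binary FLUS. Someone working from the SAP would report a comparison of mean FLUS, or an adjusted odds ratio per unit of mean FLUS. These answer related but different questions and can disagree: dichotomising a score discards information, and adjustment changes what is estimated.

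The ventilation model adds further open choices: which covariates, which form of FLUS, which outcome, and whether patients with a ventilator limit are included. The last choice can matter. Patients judged unsuitable for intubation, or unwilling to have it, will mostly count as non-events whatever their scan shows, so including or excluding them can change the association.

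The protocol plans a preliminary analysis shortly after 15 May. If the documents are not aligned by then, any of these choices could be made with results in view.

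**Working it through.** **1. Primary analysis, side by side.**

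| Element | Protocol | SAP |
|---|---|---|
| FLUS variable | Binary, pneumonia 1/0 | Zone scores 0-3 and their mean; no binary variable |
| Outcome | Intubation, yes/no | Ventilator treatment (table); COVID-19-related need for mechanical ventilation (prose) |
| Method | Chi-square, 5% | t-test or rank-sum; univariable and multivariable logistic regression; no chi-square |
| Population | No restriction stated | No ventilator limit (multivariable model in the table only); none stated in the prose |

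The number of SAP analyses that match the protocol's primary endpoint in both FLUS form and test is 0.

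**2. Covariates of the ventilation model.**

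| Covariate | Protocol | SAP table | SAP prose |
|---|---|---|---|
| Age | yes | yes | yes |
| FLUS | binary or ordinal | mean | mean |
| Oxygen saturation | yes | yes | no |
| SARS-CoV-2 status | yes | no | no |
| Sex | no | yes | yes |
| Comorbidity | no | no | yes |
| Oxygen administration | no | no | yes |
| Number listed | 4 | 4 | 5 |

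The union has 7 covariates. The intersection has 2, age and FLUS, and FLUS is not in the same form throughout. No two lists are identical. The SAP also disagrees with itself: the table has saturation and no comorbidity or oxygen administration, and the prose has the reverse.

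**3. Side note on the number of variables.** The protocol's Sample size section asks for 10-15 events per variable and 50-75 events, and it uses a 20% intubation rate.

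- Implied number of variables: 50/10 = 5 and 75/15 = 5.
- Participants: 75/0.20 = 375, which reproduces the lower end of the stated 375-400. The upper end corresponds to 400 x 0.20 = 80 events.
- With the four variables that the protocol actually names: 4 x 10 = 40 to 4 x 15 = 60 events, or 40/0.20 = 200 to 60/0.20 = 300 participants.

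So the sample-size statement fits a five-variable model, while the protocol's own list has four.

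**The case against.** The best defence is that the SAP's reference to the main analysis sits under Building Prediction Models, and the next sentence contrasts it with secondary outcomes fitted by the same model. It can fairly be read as the main prediction model, not as a new primary analysis. The protocol also plans a logistic model of intubation and sizes the study on it, and the SAP does examine FLUS against ventilation. This stands, and it narrows the point: the question is covered, but the FLUS form and the test are not. It does not restore the missing analysis. The protocol's allowance for an ordinal FLUS result applies to the prediction model only.

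A reader might infer three stronger things that the documents do not support.

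- *That the primary endpoint was deliberately replaced, or changed after data were seen.* The two documents carry the same date, the SAP does not say it supersedes the chi-square, and nothing shows that outcome data had been examined.
- *That the plan breaches its own rule of 15 events per variable.* The SAP says the variables will be limited and prioritised to suit the study size, so fewer events would mean fewer variables. On the plan's own figures, 375-400 participants at 20% give 75-80 events. That meets 4 x 15 = 60 and 5 x 15 = 75 in the whole cohort. The protocol also divides the data set for development and validation, but it gives no ratio, and neither document says that the SAP's minimum applies to the development part alone.
- *That silence on population contradicts the SAP table.* Silence is not contradiction, and the documents do not settle which population is right. What can be asked is that it be stated.

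**Conclusion.** The concern holds. Following the SAP to the letter never yields the protocol's primary result, and the ventilation model has three covariate lists, three outcome wordings and a stated population in only one place. This is a conflict between and within the documents, not just missing detail. It must be fixed because it touches the primary result itself.

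The conclusion rests on the wording alone and needs no assumption about event rates or data splitting. It does assume that the supplied text is the full SAP, since no redaction is marked where the analysis would be expected. The size of any effect on the results cannot be calculated from the documents. The mismatch of five variables against four is minor and is a matter of consistency.

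**What to change.** Before any data are analysed, including the preliminary analysis planned for shortly after 15 May:

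1. Add the binary FLUS by intubation chi-square to the SAP as the primary analysis, with its population stated, and label the mean-FLUS tests and all logistic models secondary. Alternatively, if the sponsor prefers mean FLUS, amend the protocol's primary endpoint and test to match.
2. For the ventilation model, write one covariate list, one form of FLUS, one outcome definition and one population, identical in the protocol, the SAP table and the SAP prose. Report the other population (with or without patients who have a ventilator limit) as a sensitivity analysis.
3. Make the number of variables agree with the sample-size statement.

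The cost is a few sentences in the SAP, and in the protocol if the endpoint changes. One of the two analyses loses its claim to primary status. No new data are needed, because the binary FLUS code, intubation and treatment limitations are already collected under the protocol.
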